17.7.2 CHIKV Screening

A CHIKV baseline Screening Sample (5.0 mL) will be obtained from ALL subjects at Visit 0 (Screening Visit) for CHIKV-specific ELISA testing for subjects by baseline serostatus.

17.7.3 COVID-19 Sample

A COVID-19 Sample [5.0 mL] will be obtained from all subjects at Visit 1 (Day 1), Visit 3 (Day 29), Visit 5 (Day 180) and at the ET for retrospective serological Sars-CoV-2 specific antibody testing.

17.7.4 Baseline Sample

A Baseline Sample [10.0 mL] will be drawn from all subjects at Visit 1 (Day 1) for retrospective investigation of potential pre-existing antibodies including but not limited to other alphaviruses (i.e. Mayaro), dengue or Zika. Such assessments may occur at laboratories other than the central laboratory used for analysis of safety samples.

17.7.5 Assessment of Laboratory Values

Laboratory values will be evaluated according to the Toxicity Grading Scale for Healthy Adult and Adolescent Volunteers Enrolled in Preventive Vaccine Clinical Trials (Food and Drug Administration). For the individual toxicity criteria refer to Section 24.3.

Laboratory assessments for which no severity grading is described in Section 24.3 are graded as described in Section 17.2.1.1 upon investigator's judgment.

The Investigator's assessment of each abnormal laboratory value, including its clinical significance, is to be recorded in the eCRF:

- Abnormal laboratory assessments that are considered clinically relevant, in the opinion of the Investigator, need to be documented as unsolicited AEs and assessed further for severity according to the toxicity grading scale provided in Section 24.3, causality and other assessments done for unsolicited AE (see Section 17.2.1).
- Abnormal laboratory assessments that are considered a symptom of an underlying AE or part of a syndrome that is reported as AE (e.g. presence of blood cells in urine in a person diagnosed with urinary tract infection) do NOT additionally need to be documented as unsolicited AE, but a respective comment should be added to the underlying AE.

Additional tests and other evaluations required to establish the significance or etiology of an abnormal laboratory result, or to monitor the course of an AE should be obtained when clinically indicated. Any abnormal value that persists should be followed at the discretion of the Investigator.

17.8 Viremia

Subjects will return to the study site to collect plasma samples from all subjects on the vaccination Day 1 and on Days 8 and 29 (Visit 1-3), and if applicable at the ET Visit. Viremia plasma sample will be obtained from all subjects for a clinically indicated retrospective investigation of viremia by quantitative RT-PCR (RT-qPCR). The retrospective analysis will be conducted if deemed necessary by the Data Safety Monitoring Board upon clinical indication.

Viremia will be analysed in plasma samples. Blood [8.0 mL] will be collected by venous puncture. Samples will be shipped on dry ice at -70°C, viral RNA will be isolated and viral CHIKV RNA will be amplified specifically by RT-qPCR.

17.9 Adverse Events of Special Interest (AESI)

In addition to nonspecific transient muscle pain and joint pain that may occur after vaccination with any vaccine, subjects will be carefully monitored for signs and symptoms suggesting an acute stage CHIKV-associated event.

If a subject develops symptoms suggestive of CHIKV infection, he/she will be asked to contact the site immediately for clinical evaluation at an unscheduled visit.

Therefore, the following cluster of symptoms with or without remissions or exacerbations will receive particular consideration:

1. Fever ($\geq 38.0^{\circ}\text{C} / 100.4^{\circ}\text{F}$ measured orally);

AND

2. Acute (poly)arthralgia/arthritis most frequently in the extremities (wrists, ankles and phalanges, often symmetric), back pain and/or neurological symptoms (e.g. confusion, optic neuritis, retinitis/uveitis meningoencephalitis or polyneuropathy) and/or cardiac symptoms (e.g. myocarditis);

OR

One or more of the following signs and symptoms: macular to maculopapular rash (sometimes with cutaneous pruritus (foot arch) and edema of the face and extremities), polyadenopathies;

AND

3. Onset of symptoms 2 to 21 days after vaccination;

AND

4. Duration of event ≥ 3 days.

Any suspected clinical case of CHIKV-associated event shall be referred to a clinical expert, be evaluated according to standard diagnostic procedures and treated according to current medical standard until resolved or stabilized. For more detailed information please refer to: French guidelines for the management of chikungunya - acute and persistent presentations (Simon, Javelle et al. 2015).

Additionally, subjects presenting with acute arthralgia within 2 to 21 days post-vaccination will be followed-up until resolution and monitored for recurrences until the end of the study.

A blood sample for laboratory investigation will be taken upon presentation of the subject. Testing may include but is not limited to rheumatoid factor (RF), anticitrullinated protein antibody (ACPA), Ferritin and CRP. Retrospective investigation of a pre-vaccination sample may be considered for a thorough causality assessment.

Suspected CHIKV-associated events do not constitute a reason for withdrawal from the study.

17.10 Adverse Event Reporting Procedures

17.10.1 Serious Adverse Event

Any SAE should be reported to the Safety Desk by fax or email within 24 hours after the Investigator has become aware of the event. Under certain circumstances the initial notification could be done by phone, but nevertheless a written SAE Report Form has to be submitted to the Safety Desk within 24 hours (see Section 3).

Correct SAE reporting will have to cite a diagnosis or a symptom. Any diagnosis and any symptom is regarded as separate SAE. However, if the Investigator considers several symptoms to be in the context of one underlying diagnosis, he/she may specify the diagnosis as the reportable SAE and describe the attendant symptoms in one single appropriate SAE report.

Medical or diagnostic procedures due to an underlying disease or symptom are not considered an AE but a consequent measure following an AE. A correct SAE report will therefore have to specify the disease or symptom as the reportable AE and the medical or diagnostic procedure as action taken.

In addition, expedited and periodic reporting to Competent Authorities and IRBs will be performed in accordance with local requirements. Further reporting details can be found in the study-specific SAE procedure which is in accordance with respective US/EU requirements, International Conference on harmonization (ICH) GCP, national laws and site-specific requirements. SAEs that are considered as probably or possibly related and additionally are unexpected need to be reported according to the requirements for suspected unexpected serious adverse reactions (SUSARs).

SAE reports will be reviewed by a study site's physician, the Safety Desk, the Study Medical Monitor, the Sponsor and the independent DSMB.

Beyond study end, if the investigator becomes aware of SAEs that are fatal, life-threatening or suspected to be related to study treatment will continue to be reported until 6 months after the last study visit of the respective subject (i.e. Visit 5).

17.10.2 Adverse Events of Special Interest (AESI)

Any AESI should be reported to the Safety Desk by fax or email within 48 hours after the Investigator has become aware of the event. Under certain circumstances the initial notification could be done by phone, but nevertheless a written AESI Report Form has to be submitted to the Safety Desk within 48 hours (see Section 4).

Subjects will be carefully monitored for development of AESIs. A cluster of symptoms (see 17.9) associated with CHIKV infection, are defined as AESI. In case an AESI is identified, the Investigator will complete the AESI Report Form with all available information including medical records. This information will be provided to the DSMB. The DSMB will perform a thorough review of each case and advise whether additional clinical work-up is required.

The DSMB will conduct a final adjudication of all AESIs and will assess whether cases were new in onset and whether there is any relationship to administration of the study vaccine. Narratives with detailed case descriptions will be provided for all AESIs.

17.10.3 Pregnancy

The risk of maternal to fetal transmission of chikungunya virus during pregnancy cannot be excluded. Thus, women must not become pregnant during the first three months post-vaccination.

Reporting requirements start with administration of the vaccination until study completion (or ET Visit). All pregnancies that occur during the clinical study period will be followed-up for three months after delivery or termination of the pregnancy. Any effect on either mother or fetus should be determined. A pregnancy which led to a congenital anomaly/birth defect must be followed-up by the Investigator longer or until resolution or stabilization. Duration of prolonged follow-up will be decided on an individual basis and in accordance with the Sponsor. The Investigator will prepare a narrative on the course of the pregnancy and the outcome.

The Investigator should report pregnancies within 24 hours of being notified using the Pregnancy Report Form. Reporting procedures are similar to SAE reporting procedures (contacts and processing), although a pregnancy is not considered an SAE (see Section 5).

If a seriousness criterion applies in addition to the pregnancy (e.g. hospitalization, congenital anomaly/birth defect) the pregnancy qualifies as an SAE. In such case a Pregnancy Report Form and an SAE Report Form have to be filled out.

17.11 Safety Monitoring

17.11.1 Data Safety Monitoring Board

An independent Data Safety Monitoring Board (DSMB) will be utilized for this study. The DSMB will consist of four voting members who will be selected based upon their expertise with and understanding of infectious diseases, vaccines, clinical research and/or skills and knowledge in clinical medicine. The DSMB will meet to review accumulating safety data on a regular basis until all subjects have received the vaccination at Day 1 and until all subjects have completed Visit 2 or 3. In addition, the DSMB will periodically review accruing safety information throughout the study, as applicable. A meeting of the DSMB may be called at the discretion of the Sponsor, e.g. to address any safety concerns arising during the conduct of the study.

The DSMB will ad hoc review cases of SAEs, AESIs and severe (Grade 3) solicited AEs. The DSMB will periodically review listings and summary tabulations of SAEs, Deaths, Solicited AEs, Unsolicited AEs.

A DSMB charter including a detailed description will be prepared.

Responsibilities of the DSMB

- Provides independent monitoring of safety issues, which means it reviews and evaluates all SAE reports and study discontinuations for: (i) increases in frequency of SAEs and study discontinuations within the study; and (ii) SAEs in the study sample compared with the population based on what is known from the literature;
- Reviews data produced from the study upon the Sponsor's request to determine whether the conditions on which study design is based have remained the same or have changed. If changed, the DSMB will suggest whether or not the changes mandate changes to the protocol and suggest a protocol amendment;
- Upon the Sponsor's request, meets for discussion and gives recommendations to the Sponsor as to whether the study should progress unchanged, or the study requires changes, or the study should be terminated prematurely;
- Can propose an unplanned safety analysis of clinical trial data;
- Can suggest unscheduled visits for specific evaluations for individual cases reviewed.

17.11.2 Sponsor

Until the last subject reached Day 29, listings of available blinded safety data will be closely reviewed by the Sponsor to identify any potential safety concerns.

17.11.3 Investigator

To ensure information exchange on safety across sites, Investigators will be provided with safety information pertaining to all severe (Grade 3) AEs and SAEs reported in the eCRF.

18. STATISTICS

18.1 Sample Size Justification

The sample size is selected to allow for a demonstration of Lot-to-Lot consistency based on the primary endpoint, CHIKV-specific neutralizing antibody titers as determined by microneutralization (μ PRNT) assay on Day 29 post-vaccination. The primary analysis will demonstrate equivalence between the three treatment groups based on a comparison of GMTs.

402 randomized subjects (i.e. 134 per batch) will ensure that the three pair-wise comparisons have an overall power of approximately 90% based on a two-sided significance level of 5%, an assumed SD of 0.32 (on a log10 scale), and acceptance margins of [REDACTED] for the GMT ratios, while correcting for an assumed drop-out rate of 10%, 5% of subjects with major protocol deviations and 2% expected to be baseline positive for CHIKV.

18.2 Datasets and Analysis Cohorts

The full analysis set contains all subjects who were randomized and received at least one vaccination. Subjects will be analyzed as randomized.

The safety analysis set contains all subjects who entered into the study and received at least one vaccination. Subjects will be analyzed as treated.

The per protocol (PP) analysis set contains all subjects who were baseline negative for CHIKV antibodies and have received the vaccination and have evaluable immunogenicity data at baseline and the time point for the primary endpoint without a major protocol violation. Examples that may lead to exclusion from the PP population are provided here, further criteria may be defined in the Statistical Analysis Plan (SAP):

- Subject has a known or suspected defect of the immune system that can be expected to influence the immune response to the vaccine, such as subjects with congenital or acquired immunodeficiency, including infection with HIV, status post organ transplantation or immuno-suppressive therapy within 4 weeks prior to Visit 1. Immuno-suppressive therapy is defined as administration of chronic (longer than 14 days) prednisone or equivalent ≥ 0.05 mg/kg/day within 4 weeks prior to study entry, radiation therapy or immunosuppressive cytotoxic drugs/ monoclonal antibodies in the previous 3 years; topical and inhaled steroids are allowed;

- Subject is positive for human immunodeficiency virus (HIV), hepatitis B surface antigen (HBsAg) or hepatitis C virus (HCV);
- Subject has received the wrong (not according to randomization) or no IMP.

These criteria for protocol violations are identified at the time of planning the study. However, during the course of the trial unforeseen events may occur or new scientific knowledge may become available, therefore final decisions on whether a protocol violation could impact on the immune response and thus lead to exclusion from the PP population will be made by the sponsor on a case by case basis in a blinded manner (prior to study unblinding). Sample testing issues may also lead to exclusion from the PP analysis for particular time points.

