^c Prior vaccination against relevant traveler diseases should be documented in the Medical History, i.e. YF and JEV.
^d At the screening visit, a physical examination will be performed on the following body systems being described as normal or abnormal: general appearance, head and neck, eyes and ears, nose and throat, chest, lungs, heart, abdomen, extremities and joints, lymph nodes, skin, and neurological. At subsequent visits, a symptom-driven physical examination will be performed, i.e. only in case symptom is reported by the subject, a symptom-based assessment of the affected body system(s) will be performed. A Hand Stiffness and mobility examination will be performed at all study visits irrespective of prior symptoms.
^e Vital signs will include systolic and diastolic blood pressure and pulse rate while seated and at rest, and body temperature measured orally before vaccination. In addition, after an observation period of 30 minutes following vaccination pulse rate as well as blood pressure while seated and at rest will again be assessed.
^f A **serum** pregnancy test will be performed for all female subjects of childbearing potential at the screening visit only and a **urine** pregnancy test will be done prior to vaccination at Visit 1 and at indicated visits [blood: 3.0 mL].
^g A CHIKV Screening Sample (5.0 mL) will be obtained at Visit 0 (Screening Visit) for CHIKV-specific ELISA testing for baseline serostatus.
^h Safety laboratory sample for standard safety laboratory assessments according to Section 17.7.1.
ⁱ A positive HIV test obtained by ELISA will have to be confirmed by a second method (e.g. Western blot or PCR).
^j A Baseline Sample will be drawn for retrospective investigation of potential pre-existing antibodies including but not limited to other alphaviruses (i.e. Mayaro) or Dengue and ZIKA.
^k Immunogenicity sample for CHIKV-specific neutralizing antibody titer evaluation, development of further assays or retrospective safety analysis. For further information on the preparation, storage and shipment of blood samples please refer to the instructions in the respective Laboratory Manual provided in the Investigator File.
^l Viremia plasma sample for clinically indicated **retrospective** investigation of viremia by RT-qPCR.

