18.4.1 Primary Endpoint

The primary immunogenicity analysis will be a comparison of the GMTs in the per-protocol (PP) analysis set between the VLA1553 Lots 1, 2 and 3 at Day 29 (i.e. 28 days post-vaccination) by ANOVA (factor Lot, covariate study site). The ANOVA model will be applied to the log10-transformed μ PRNT values of the three Lots and the 95% CIs for the pair-wise ratios of the GMTs will be obtained by taking the anti-log of the resulting 95% CIs for the least square means differences. If these three pairwise 95% CIs for GMT ratios are all between [REDACTED], equivalence between the three commercial batches will be postulated.

The analysis will be performed on the PP population who were baseline negative for CHIKV antibodies and will be repeated on the full analysis set.

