9.0 Study Estimands

9.1 Target Population

The target population consists of healthy subjects aged 18 to 45 years receiving one of three lots of VLA1553, which is a candidate vaccine intended to prevent CHIKV infections in the general population living in endemic regions, as well as to serve as a prophylactic measure for travelers to epidemic areas or areas at risk for an upcoming outbreak or ongoing endemic transmission. Subjects are screened for their CHIKV serostatus by ELISA at study entry; subjects who test positive for CHIKV as measured by ELISA assay are excluded from the PP analysis set. For the primary and secondary endpoint analysis the μ PRNT assay is used to determine neutralizing antibody titers.

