9.4.3 Per Protocol Analysis Set

The per protocol (PP) analysis set contains all subjects who were baseline negative for CHIKV antibodies as determined by ELISA assay, have received the vaccination and have evaluable immunogenicity data at baseline and the time point for the primary endpoint without a major protocol deviation. This analysis set will be the primary analysis set for immunogenicity analyses. Subjects will be analyzed in the PP analysis set according to the study arm they have been randomized to.

9.4.4

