11.6.3 Seroconversion

Seroconversion is defined as a CHIKV-specific [REDACTED] for baseline μ PRNT negative subjects (PP, sPP1 for definition see section 9.4.3 and 9.4.4). Seroconversion for baseline μ PRNT positive subjects (included in PP) is defined as a [REDACTED] increase over baseline.

The seroconversion rate (SCR) is defined as the proportion of subjects meeting the criteria for seroconversion at the relevant study timepoint.

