13.4.3.2 Seroprotection Rate

The number and percentage of subjects meeting the criteria for seroprotection will be presented for each study timepoint and treatment group. The denominator for the percentage will be the number of baseline negative μ PRNT subjects with non-missing NT values at each timepoint. Two-sided exact (Clopper-Pearson) 95% CIs for the seroprotection rate (SPR) will be presented.

The treatment groups will be compared using Fisher's Exact test. In addition, the pairwise difference in risk between the three treatment groups, and exact two-sided 95% CIs for the pairwise differences in risk between treatment groups will be presented.

This summary will be repeated by titer threshold, evaluating the number of baseline negative subjects meeting the criteria μ PRNT₅₀ \geq x, where x takes the values [REDACTED]

Bar charts of the percentage of subjects meeting the seroprotective criteria will be produced by study visit and treatment group.

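### The primary lot comparison keeps subjects who are already µPRNT-positive on Day 1 but has no model term for it; adding one removes avoidable variance at almost no cost

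*Protocol*

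**What the plan says.** **Who is in the decision set.** Under Protocol 18.2 the PP set "contains all subjects who were baseline negative for CHIKV antibodies and have received the vaccination and have evaluable immunogenicity data at baseline". That section does not name the assay behind baseline negativity, but Protocol 15.4.1 does: a screening sample is taken "for CHIKV-specific ELISA testing for baseline serostatus". SAP 9.4.3 defines PP as "baseline negative for CHIKV antibodies as determined by ELISA assay", and SAP 9.1 states the matching exclusion: "subjects who test positive for CHIKV as measured by ELISA assay are excluded from the PP analysis set". SAP 9.2 restricts the primary endpoint in the same way.

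**Baseline µPRNT-positive subjects.** SAP 11.6.3 gives them their own seroconversion rule and places them in PP: "positive subjects (included in PP) is defined as a" (the size of the increase is blacked out). The same section links µPRNT-negative subjects to both PP and a set called sPP1, whose definition in 9.4.4 is blacked out.

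**The primary model.** Protocol 18.4.1 compares Day 29 GMTs "by ANOVA (factor Lot, covariate study site"). SAP 13.4.2 has the same two terms, lot and center, and decides equivalence on PP with a repeat on the full analysis set.

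**What is available.** The µPRNT is run on Day 1 samples (Protocol 16, SAP 11.6), and PP requires evaluable baseline immunogenicity data. Each PP subject's Day 1 status is therefore known.

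**Elsewhere in the SAP.** Seroprotection is confined to µPRNT-negative subjects (13.4.3.2: "The denominator for the percentage will be the number of baseline negative" by µPRNT). Section 13.4.3.1 compares Day 1 GMTs between lots and analyzes geometric mean fold increase (GMFI) in the same way as GMTs.

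**The concern.** The primary outcome is the µPRNT titer. A subject who already has neutralizing antibody in that assay on Day 1 may reach Day 29 with a titer that partly reflects earlier immunity, so it measures the lot less cleanly than a naïve subject's titer does. Protocol 11.1 states the purpose in terms of a CHIKV-naïve population. Protocol 10.3.2 reports that re-vaccinated Phase 1 subjects showed neither vaccine viremia nor an anamnestic response. That supports the mechanism, but those subjects were vaccine-primed, so it says nothing about the size of the effect in ELISA-negative people with some neutralizing activity.

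If such subjects have a different mean Day 29 titer, they widen the residual SD and, when unevenly spread by chance, move a GMT ratio. Both make it harder to place all three confidence intervals inside the margins. The sample-size allowance of 2% baseline positives is for ELISA positives (SAP 8.1), and no allowance for ELISA-negative, µPRNT-positive subjects is visible. A known baseline predictor of the outcome is left out of the model although it is already measured.

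**Working it through.** **Inputs from the documents (Protocol 18.1, SAP 8.1).** 134 randomized per lot; SD 0.32 log10; two-sided 5%; about 90% overall power for three pairwise tests; losses of 10%, 5% and 2%.

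**Evaluable per lot.** 134 × (1 − 0.17) = 111.2. Taken multiplicatively, 134 × 0.90 × 0.95 × 0.98 = 112.3. I use 111.

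**The plan's own figure.** The margin is blacked out, so 90% cannot be reproduced from the visible inputs alone. Simulated joint power at 111 per lot with equal lots and no site term:

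| Assumed margin (fold) | Joint power |
|---|---|
| 1.25 | 5% |
| 1.33 | 37% |
| 1.4 | 68% |
| 1.49 (0.173 log10) | 90% |
| 1.5 | 91.6% |
| 2.0 | >99.9% |

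A margin close to 1.5-fold fits the stated 402 subjects and 90%. Below I use 0.173 log10, which returns the stated power.

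**Assumed, because the documents do not say.** Share p of PP subjects who are ELISA-negative but µPRNT-positive: 0.5–3%. Difference d in their mean Day 29 log10 titer: 0.3–0.5, with 1.0 as an extreme.

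**Residual SD without adjustment** = √(0.32² + p(1 − p)d²):
- p = 2%, d = 0.5: √(0.1024 + 0.0049) = 0.328
- p = 3%, d = 0.5: √(0.1024 + 0.0073) = 0.331
- p = 2%, d = 1.0: √(0.1024 + 0.0196) = 0.349
- p = 3%, d = 1.0: √(0.1024 + 0.0291) = 0.363

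A status term returns the residual SD to 0.32. It costs one of about 3 × 111 − 3 = 330 residual degrees of freedom.

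**Joint power by simulation:**

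| p, d | Kept, no term | Excluded | Kept, status term |
|---|---|---|---|
| 0.5%, 0.3 | 90.1% | 90.1% | about 90% |
| 1%, 0.5 | 88.9% | 89.7% | about 90% |
| 2%, 0.5 | 88.0% | 89.1% | about 90% |
| 3%, 0.5 | 86.4% | 88.7% | about 90% |
| 2–3%, 1.0 | about 75–81% | – | about 90% |

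The gain from the term is nil at the low end and about 1, 2 and a little over 3 points in the next three rows. Exclusion recovers less because it also loses subjects. The sign of d matters little: at a 1.5-fold margin and d = −0.5, kept versus excluded is 90.2% versus 90.8% (1%) and 90.3% versus 91.3% (2%).

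**Chance imbalance.** If one lot has k more such subjects than another, the GMT ratio moves by 10^(k·d/111). For k = 3 that is 1.032 at d = 0.5 and 1.064 at d = 1.0. At a 2% share, the gap between the highest and lowest lot counts has a median of 2 and a 95th percentile of 5. For comparison, the 95% CI half-width is 1.967 × 0.32 × √(2/111) = 0.0845 log10, or about 21%.

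**False equivalence.** With one lot's true difference set at a 1.5-fold margin in naïve subjects, and shares of 2–5%, equivalence was declared in under 1% of runs whether the subjects were kept or excluded.

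**The case against.** **ELISA is a deliberate and consistent choice.** A reader might infer that the SAP departs from the protocol. It does not: the protocol already uses ELISA for baseline serostatus, and the SAP carries it through the sample size, target population, primary endpoint and PP set. This stands, so the point concerns model efficiency and not a contradiction. The narrower seroprotection denominator is not an inconsistency either. A threshold endpoint can be met before vaccination, so it needs that restriction; a GMT ratio between randomized lots does not.

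**No bias.** A reader might infer that these subjects could favor a lot or produce a false consistency claim. Randomization balances them in expectation, and the simulated false-equivalence rate stays below 1%. What is at stake is power, which is mainly the sponsor's risk.

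**A sensitivity analysis may already exist.** SAP 11.6.3 attaches sPP1 to µPRNT-negative subjects only, so sPP1 is probably the µPRNT-negative part of PP. With 9.4.4 and 13.4.4 blacked out, nobody can say the plan lacks such an analysis. The GMFI and Day 1 GMT comparisons also take baseline titer into account. These are secondary, however, and none changes the primary model in 13.4.2.

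**The large losses are speculative.** Falling to about 75–81% needs a full 1.0 log10 shift, which no document supports. Even 3% exceeds the whole 2% ELISA-positive allowance, in a U.S. population that excludes past or suspected infection. This stands too.

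**A status factor can distort reported GMTs.** Default least-squares means in SAS weight factor levels equally, so each lot GMT would become a 50/50 average of negatives and a handful of positives. Pairwise ratios are unaffected. The specification has to deal with this, and it can.

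**Conclusion.** The point holds as a modest, nearly free improvement. The decision set is expected to contain baseline µPRNT-positive subjects, their status is known, and the primary ANOVA does not use it. With a 0.5–3% share, a 0.3–0.5 log10 shift, 111 per lot and a margin near 1.49-fold, adjustment recovers about 0 to 3 power points. The gain is materially larger only if the shift approaches 1.0 log10. All three drivers (share, shift and margin) are assumptions. If the true margin were much wider, power would be near 100% and the loss negligible, but the stated 90% would then not follow from the other inputs. The simulations also assume the same shift in every lot and no site effect.

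**What to change.** In SAP 13.4.2 and Protocol 18.4.1:

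- Keep PP as the decision set and add Day 1 µPRNT status (negative/positive, by the SAP's own cut-off) as a term in the primary ANOVA beside lot and center. State that the term drops out if no PP subject is positive.
- Compute least-squares means at observed margins, so that reported lot GMTs reflect the actual mix of negatives and positives.
- Repeat the primary analysis in Day 1 µPRNT-negative PP subjects as a sensitivity analysis. If the sPP1 analyses in 9.4.4 and 13.4.4 already do this, no addition is needed.

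The cost is one degree of freedom, no subjects, no new data and minor SAP wording. The change should be fixed before Part A is unblinded, so that it cannot look like a choice made after a confidence interval narrowly missed.
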